Our outcome analyses will focus on examining the acute effects and duration of intranasal ketamine treatment during inpatient psychiatric hospitalization. As a primary outcome, we will examine the efficacy of intranasal ketamine for preventing suicidal behavior and ideation among adult patients in a current depressive episode at day 1. Our primary outcome analysis seeks to answer two questions: 1) will intranasal ketamine work acutely compared to placebo, and 2) how long will this effect persist? Effect sizes will be calculated for intranasal ketamine treatment. In the primary outcome analysis, two dichotomous primary outcome measures will be examined in the evaluation: 1) the presence or absence of suicidal ideation, and 2) the presence or absence of suicidal behavior as measured using the C-SSRS and SSI. Our secondary outcome analysis will include an examination of 1) the effects of intranasal ketamine for suicidal ideation while controlling for improvements in depression and other dimensions 2) the potential role of recent alcohol abuse and previous alcohol dependence in the rapid anti-suicidal effects of intranasal ketamine. The symptom severity ratings of SSI, the C-SSRS total score and, as well as changes in MADRS scores will be utilized as primary and secondary outcomes, respectively. Normality assumptions for continuous variables will be examined. Baseline characteristics will be compared between responders and non-responders with the Mann-Whitney U test for continuous variables and the chi-square test for categorical variables. Changes between two time-points for continuous variables were tested with paired t tests, and associations between continuous variables will be quantified with the Spearman correlation coefficient. Random effects models will be performed to quantify changes in clinical score and its component items over time and to compare temporal differences between eventual responders and non-responders.

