Analyses of cross-sectional data with missing values will utilize multiple imputation (Proc MI and Proc MIANALYZE, SAS v. 9.3), while longitudinal analyses will rely on maximum likelihood (in the Bayesian context). Multiple imputation, maximum likelihood, and explicitly modeling missing data in the Bayesian approach are all robust to data missing at random. Sensitivity analyses will permit evaluation of the robustness of findings to missing data assumptions. Pattern-mixture modeling methods will address any identified non-ignorable missing data patterns.

Preliminary data analyses will inspect baseline group differences as well as correlations between baseline covariates and specified criterion variables. Baseline covariates demonstrating a correlation

IRB NUMBER: HSC-MS-17-0903

IRB APPROVAL DATE: 10/09/2019

with both predictors and outcome variables, meet criteria for being potential confounders, and will result in two sets of analyses: one in which the relevant variable is included as a covariate and one in which it is not. This will determine the degree to which any group differences might confound conclusions regarding treatment. Analyses will proceed in parallel using conventional, Frequentist and Bayesian approaches. Frequentist results yield the probability of the observed data, or data more extreme, given that the null hypothesis holds. Bayesian results yield the probability that an alternative holds. Eleven patients per group are required using confidence level of 95% (with $P<0.05$, two-tailed) and power 0.8, based on previous studies using ketamine for depression in placebo-controlled studies reporting response rates of 60% with ketamine and 10% with placebo. The study was designed to detect a moderate to large difference ($d=0.7$) between ketamine vs placebo, based on previous studies using IV ketamine (Wilkinson et al 2018). Treatment effects may be also quantified as mean differences between groups and associated effect sizes are based on standardized mean difference (Cohen's d). All statistical tests were two-sided with an alpha set at 0.05. All analyses were performed using SPSS v. 20 (SPSS Inc., USA) and SAS (version 9.2; SAS, Cary, North Carolina).

References

Andrade C. Intranasal drug delivery in neuropsychiatry: focus on intranasal ketamine for refractory depression. *J Clin Psychiatry*. 2015 May;76(5):e628-31.

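### No between-arm analysis is named as deciding the primary comparison of SSI change at 24 h, and baseline SSI can enter only through a correlation screen

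*Combined protocol and SAP*

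**What the plan says.** The Design section names change in SSI at 24 h as the primary efficacy outcome, and the primary hypothesis is framed against placebo on the same measure. The Statistics section opens its primary analysis by asking "will intranasal ketamine work acutely compared to placebo". It also lists two dichotomous primary measures, the presence or absence of suicidal ideation and of suicidal behavior.

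The methods it then describes for continuous outcomes are:

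- "Changes between two time-points for continuous variables were tested with paired t tests".
- "Random effects models will be performed to quantify changes in clinical score and its component items over time". The only group contrast given for these models is the one between patients who eventually respond and those who do not.
- "Treatment effects may be also quantified as mean differences between groups", with Cohen's d.

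Mann-Whitney and chi-square tests are reserved for the baseline characteristics of responders against non-responders.

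On covariates, a preliminary step looks for baseline variables that correlate "with both predictors and outcome variables, meet criteria for being potential confounders, and will result in two sets of analyses", one including the variable and one leaving it out. The stated purpose is: "This will determine the degree to which any group differences might confound conclusions regarding treatment". The next sentence adds: "Analyses will proceed in parallel using conventional, Frequentist and Bayesian approaches".

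**The concern.** A randomised trial needs one between-arm analysis, fixed in advance, that settles its primary question. Here a reader can identify the outcome and the comparison but not the analysis. A t test on change, a t test on the 24 h score, an ANCOVA and a mixed model would all be compatible with the text, in either a frequentist or a Bayesian version. If the choice is made once the data are in, the nominal 5% error rate no longer holds.

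The test actually named for change between time-points cannot fill the gap. The Study Population section gives supportive care to both arms during the 48 hours, so improvement within the ketamine arm does not separate drug from setting.

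The covariate rule is a lesser matter. Baseline SSI is usually the obvious covariate for 24 h SSI, yet it would enter only if it happened to correlate with the predictors (undefined, most naturally treatment arm) as well as with outcome. Using a change score subtracts baseline, which is not the same as adjusting for it.

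**Working it through.** **1. Which contrast each named method serves**

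| Method in Statistics | Contrast stated |
|---|---|
| Mann-Whitney, chi-square | baseline characteristics, responders v non-responders |
| Paired t test | two time-points, same patients |
| Random effects models | change over time; responders v non-responders; no arm or arm-by-time term stated |
| Mean difference, Cohen's d | between groups, but optional and without a test or model |

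None is stated as the arm comparison of SSI change at 24 h.

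**2. The plan's own sample size figure.** For response rates of 60% and 10%, two-sided 0.05 and power 0.8, the unpooled formula gives (0.6×0.4 + 0.1×0.9)×(1.960+0.842)²/0.5² = 10.36, rounded up to the stated 11 per group. It rests on response rates, so it does not imply a test for SSI change.

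**3. Error rate if the analysis is chosen afterwards.** Simulated trials with no drug effect, normal data, equal SDs, baseline-to-24 h correlations 0.3 to 0.7, at 30 v 30 and 30 v 15:

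- each analysis fixed in advance: about 0.05;
- better of change score and ANCOVA: about 0.065 to 0.08;
- best of change score, ANCOVA and raw 24 h score: about 0.09 to 0.10.

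**4. Paired test within the ketamine arm.** Suppose, as an assumption, that both arms improve equally by 0.7 SD with no drug effect, with equal SDs. Then the SD of change is √(2(1−ρ)) and the noncentrality for 30 patients is 0.7×√30/√(2(1−ρ)), or 3.24, 3.83 and 4.95 at ρ = 0.3, 0.5 and 0.7. The test is significant in about 88% to 99.7% of such trials.

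**5. Power by choice of analysis.** From the documents: d=0.7 and two-sided 0.05. The arm sizes conflict. Description of Study Populations gives 30 ketamine and 15 placebo (45, against a stated total of 60), Design gives 1:1, and the text after the list of measures gives about two thirds ketamine. Both 30 v 30 and 30 v 15 are shown. Assumed: d on the 24 h SD (set to 1), baseline SD = k, correlation ρ, no dropout, no alcohol effect on outcome.

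- Variance of change = 1 + k² − 2kρ, with N−2 df.
- ANCOVA variance = (1−ρ²)×(1 + 1/(N−c−3)), with N−2−c df and c=2 covariates.
- Noncentrality = (0.7/SD)×√(n₁n₂/(n₁+n₂)).

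Example, 30 v 30, k=1, ρ=0.3. Change: variance 1.40, noncentrality (0.7/1.183)×3.873 = 2.29, power 62%. ANCOVA: 0.91×(1+1/55) = 0.927, noncentrality (0.7/0.963)×3.873 = 2.82, power 79%.

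| Power % at ρ = 0.3/0.5/0.7 | 30 v 30 | 30 v 15 |
|---|---|---|
| ANCOVA | 79/86/96 | 61/69/85 |
| Change, k=1.0 | 62/76/93 | 45/58/80 |
| Change, k=0.7 | 73/85/96 | 55/68/86 |
| Change, k=0.5 | 78/87/95 | 60/70/83 |
| Raw 24 h score | 76 | 58 |

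The plan does not say which SD d refers to. If it is the SD of change, change-score power at 30 v 30 is 76% throughout and ANCOVA is 91/86/82% (k=1.0), 82/77/75% (k=0.7) or 77/75/78% (k=0.5).

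**6. The correlation screen.** Under randomisation any correlation of baseline SSI with arm is chance, so a screen at level p passes it at most a fraction p of the time. The plan gives no threshold. Simulation gives selection in at most about 5% of trials at p<0.05 and 20% at p<0.20. At the two layouts above, the analyses with and without baseline SSI disagree on significance in at most 2.4% and 8.7% of all trials respectively. If either result may count when the variable is selected, null rejection is 0.046 to 0.057.

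**The case against.** The plan plainly intends an arm comparison, and a reasonable analyst would supply one. The random effects framework could carry an arm-by-time term. The covariate rule sits under preliminary analyses and states a purpose: it is a confounding check reported both ways, not a way of picking the primary model. The power figures rest on correlations and SD ratios that the documents do not give.

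Much of this stands. The intent is there; what is missing is the model, its covariates and which result decides. Read as a confounding check, the rule is harmless to error, but it still leaves open which set of results governs. The textual gap does not depend on any power figure.

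Three stronger readings are tempting and should not be drawn. A reader might infer that the screen itself inflates type I error; the 0.046 to 0.057 above does not support that, and the inflation comes from the open choice of between-arm analysis. A reader might infer that the sponsor means to decide on within-arm paired tests; the text names them for change between time-points and does not make them the primary analysis. A reader might infer that ANCOVA always gains; with a smaller baseline SD, or with d on the change SD, it can equal or fall marginally below the change score.

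**Conclusion.** The concern holds: no between-arm analysis of SSI change at 24 h is named as deciding. The main cost is to error control, about 0.065 to 0.08 for a free choice between two reasonable analyses and about 0.09 to 0.10 among three, assuming normal data and equal SDs. The covariate rule is subordinate. Its cost is precision, ranging from nil (or a marginal gain for change) to as much as 17 points of power (62% v 79% at 30 v 30, correlation 0.3, equal SDs, d on the 24 h SD). The documents do not fix where in that range the trial falls. None of these figures applies to the two dichotomous primary measures.

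**What to change.** For SSI at 24 h, prespecify one frequentist between-arm ANCOVA on arm, baseline SSI and the alcohol group within which Design randomises. A mixed model with arm-by-time, the same covariates and the 24 h contrast would serve equally and fits the framework already named. Then:

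- State that this result decides. Make the Bayesian analysis and other covariate models sensitivity analyses, and keep paired tests and responder contrasts exploratory.
- Drop correlation screening for this analysis.
- State the patient set: all randomised patients, as the primary objective implies, or those with comorbid alcohol use, as the primary hypothesis is worded. In the latter case the alcohol term drops out.
- Reconcile the SSI primary in Design with the dichotomous primaries in Statistics.
- Reconcile the two alcohol groups in Design with inclusion criterion 4, which read literally leaves no group without alcohol abuse.

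The cost is wording in both the protocol and the SAP, plus one or two degrees of freedom. Baseline SSI is already collected, so no new data are needed.

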Description of Study Populations: A total of 60 individuals (males and females) between the ages of 21-60 will be enrolled in the study. Two participant populations will be recruited into this protocol. Participant populations are individuals with the following conditions: 1.) current suicidal ideation and past suicide attempt under intranasal ketamine (Group 1, n= 30) and current suicidal ideation and past/recent suicide attempt under placebo (Group 2, n= 15). Group 1 will include two subgroups, with (n=15) or without (n=15) recent abuse of alcohol plus positive personal/family history for alcoholism. The study will take place at a Research Unit at the Harris County Psychiatric Center, UT Houston. Participants at acute risk will be admitted to the HCPC 2D Unit, a secure, but voluntary psychiatric unit, in which there will be nursing staff and physicians available at all hours to respond to any crisis as needed. Subjects will complete an informed consent process and will be systematically screened for inclusion and exclusion criteria. Only participants with a lifetime history of suicide attempt will be enrolled.

Design

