This study will be a double-blind, randomized, placebo controlled trial, evaluating drug-free inpatients (at least 24hs period pre-admission) with depressive episode associated with past suicidal attempt and current active suicidal ideation. Patients will be randomly assigned to intranasal ketamine hydrochloride (50 mg) or saline solution (1 to 1 in both groups, suicide or suicide plus alcohol, with a total of 4 groups). After the single intranasal administration, assessments will occur at +40 min, +240 min, +24 h (phase 1), and +48 h (phase 2). For phase 2, patient may receive their regularly scheduled daily medications if improvement less than 50%. Pts will be subsequently followed up on the suicidal ideation scores until discharge once a day with treatment as usual. This study is expected to take one year to be concluded. Medication should be applied in the first 24hs after admission. There is no approved treatment for suicidal ideation and just a few trials used ketamine for suicidal ideation, none of them evaluating the intranasal route. Thus, a placebo-controlled study is warranted to prevent potential methodological issues. The use of ketamine plus standard care would bias the evaluation of the specific antisuicidal efficacy of intranasal ketamine since standard treatments in some cases may also target suicidality and mood in the short-term.

Assessment of antisuicidal efficacy will be obtained using the Columbia-Suicide Severity Rating Scale (CSSRS) as a screening tool for inclusion (based on "yes" or "no" questions) at HCPC. MADRS item 10 score of 5 or 6 suggests active suicidal risk and will be also used as the threshold for patient inclusion in the ketamine intervention. For those enrolled, the primary efficacy outcome measure will be changes in suicide severity at 24hr post-treatment based on the Scale for Suicide Ideation (SSI) scores, which assesses presence of suicidal ideation and history of suicidal behavior. Secondary outcomes to be administered at each visit include the Montgomery-Åsberg Depression Rating Scale (MADRS), the Young Mania Rating Scale (YMRS), the Clinician-Administered Dissociative States Scale (CADSS), Snaith-Hamilton Pleasure Scale (SHAPS) Alcohol Urge Questionnaire (AUQ) and the Clinician-Administered National Institutes of Health-Brief Fatigue Inventory (NIH-BFI). Inter-rater reliability will be assessed for all ratings, with accepted kappa over 0.8.

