- 5) *Clinician-Administered Dissociative States Scale* (CADSS) is a clinician-administered measure of perceptual, behavioral and attentional changes occurring during dissociative experiences that has been tested in healthy subjects and post-traumatic stress disorder (PTSD). This scale involves 19 self-reported questions and eight observer ratings scored from 0 (not at all) to 4 (extremely). To characterize dissociative responses to ketamine, the CADSS will be sorted into five subscores with apparent face validity based on published scales that also assess dissociative states: body perception, environmental perception, feelings of unreality, memory impairment and time perception (Bremner et al 1998).
- 6) The *Snaith-Hamilton Pleasure Scale* (SHAPS) is an assessment of anhedonia, which has been extensively used by our group. The 14-item measure takes 5 minutes to complete (Snaith et al 1995).
- 7) The *Clinician-Administered National Institutes of Health-Brief Fatigue Inventory* (NIH-BFI) is an assessment of fatigue in the context of depression (Saligan et al 2015).
- 8) *Self-Report: Alcohol Urge Questionnaire* (AUQ) is a multi-item measure of self- reported urges to drink alcohol, predictor of drinking abuse and relapse (Bohn MJ, Krahn DD, Staehler BA 1995) and AUDIT/CIWA.

Although the primary aim of this study to investigate the efficacy of ketamine as a treatment for suicidal thoughts, this investigation is also designed to provide initial data for potential biomarkers of antisuicidal response and the neurobiology of the response process. Sixty six percent of all patients will

IRB NUMBER: HSC-MS-17-0903
IRB APPROVAL DATE: 10/09/2019

receive intranasal ketamine, while only 33.3% will be receiving placebo. We decided not to use active placebo (midazolam) due to the risk of increasing craving for alcohol. After the end of the trial (48hs), all patients will receive treatment as usual as well as lithium, which is a medication that has shown significant antisuicidal properties (Lewitzka et al 2015). All patients will be discharge when presenting no acute suicidal ideation based on C-SSRS and SSI.

Study Population

All study investigators and raters will be blind to assignment. Subjects will complete an informed consent process and will be systematically screened for inclusion and exclusion criteria, as follows:

Inclusion Criteria:

1. Male or female between the age of 21 and 60 years old, voluntary admission.

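### The study is said to be designed to detect d=0.7, but no allocation in the plan gives 80% unadjusted power for it, and the 11-per-group calculation uses depression response rates rather than a suicidality outcome

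*Combined protocol and SAP*

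**What the plan says.** The Statistics section gives two bases for the sample size and does not connect them.

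- The first is a calculation: "Eleven patients per group are required using confidence level of 95% (with $P<0.05$, two-tailed) and power 0.8". The plan describes the inputs to this figure as "based on previous studies using ketamine for depression in placebo-controlled studies reporting response rates of 60% with ketamine and 10% with placebo".
- The second, in the next sentence, is a target effect: "The study was designed to detect a moderate to large difference ($d=0.7$) between ketamine vs placebo". It cites a meta-analysis of intravenous ketamine and suicidal ideation, and gives neither a power nor a number of patients.

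The planned size is described in three places that do not agree.

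- Description of Study Populations: "A total of 60 individuals (males and females) between the ages of 21-60 will be enrolled in the study". The groups listed there are "under intranasal ketamine (Group 1, n= 30) and current suicidal ideation and past/recent suicide attempt under placebo (Group 2, n= 15", which add to 45.
- Design: ketamine "or saline solution (1 to 1 in both groups, suicide or suicide plus alcohol, with a total of 4 groups". With 60 patients this is 30 v 30.
- The text after the list of Clinician Administered Measures: about two thirds of patients "receive intranasal ketamine, while only 33.3% will be receiving placebo". With 60 patients this is 40 v 20.

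The primary outcome concerns suicidality throughout. In Design, "the primary efficacy outcome measure will be changes in suicide severity at 24hr post-treatment based on the Scale for Suicide Ideation (SSI) scores". The Statistics section names two dichotomous primary outcomes, suicidal ideation and suicidal behavior, and also lists SSI severity ratings among the primary outcomes.

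**The concern.** A reader would take the Statistics section to mean that the trial is adequately sized for d=0.7 on suicidality. No calculation in the plan shows this. The only worked calculation is for a different outcome, and the plan's own secondary hypothesis is that the antisuicidal effect is independent of the antidepressant effect. Depression response rates therefore cannot simply stand in for suicidality.

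What is at stake is the reading of a null result. If power were 0.8, a true d=0.7 would be missed 20% of the time. At the allocations given, the miss rate is 24% to 42%. A non-significant result could then be taken as stronger evidence against d=0.7 than the design can supply.

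**Working it through.** **Inputs.** From the Statistics section: two-sided alpha 0.05, power 0.8, response rates 0.60 and 0.10, d=0.7 (standardised, so SD = 1). The allocations are those listed above. The documents give no SSI standard deviation, no suicidal-ideation rates and no dropout allowance.

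**Step 1. Reproduce 11 per group.** Unpooled large-sample formula for two proportions:

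n = (1.960 + 0.842)² × (0.6×0.4 + 0.1×0.9) / (0.6 − 0.1)² = 7.849 × 0.33 / 0.25 = 10.36, rounded up to 11.

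Nominal power at 11 per group is Φ(0.50/√(0.33/11) − 1.960) = Φ(0.927) = 82%. The figure is therefore not an arithmetic slip, although the formula is lenient. Enumerating all outcomes at 11 v 11 gives power of 73% for the uncorrected chi-square test and 56% for Fisher's exact test. The plan names no test for this comparison.

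**Step 2. Does 11 per group support d=0.7?** No. A two-sample t-test at 11 v 11 has 35% power for d=0.7.

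**Step 3. Power for d=0.7 at the planned sizes.** Two-sided t-test, noncentrality d/√(1/n₁ + 1/n₂), n₁ + n₂ − 2 degrees of freedom:

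| Ketamine v placebo | Source | Noncentrality | Power | Chance of missing d=0.7 | d with 80% power |
|---|---|---|---|---|---|
| 30 v 15 | group sizes in Description of Study Populations | 2.214 | 58.1% | 42% | 0.91 |
| 40 v 20 | 60 patients, two thirds on ketamine | 2.556 | 71.0% | 29% | 0.78 |
| 30 v 30 | 60 patients, 1:1 | 2.711 | 76.0% | 24% | 0.74 |

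The normal approximation is slightly kinder (60.0%, 72.4% and 77.4%) and does not change the conclusion. If 45 patients were split evenly (23 v 22), power would be 63%.

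**Step 4. Size needed for 80% at d=0.7.** At 1:1, 33 v 33 gives 79.97% and 34 v 34 gives 81.2%, so 68 patients. At 2:1, 48 v 24 gives 78.9% and 50 v 25 gives 80.5%, so 75 patients. Both are before dropout.

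**Step 5. What baseline adjustment would change.** If d is in units of the 24 h SSI standard deviation and baseline SSI is a covariate, the effective d is 0.7/√(1 − ρ²), with one further degree of freedom lost. Here ρ is the correlation between baseline and 24 h SSI. Power of 80% then needs ρ of about 0.31 at 30 v 30, 0.44 at 40 v 20 or 0.64 at 30 v 15. The documents give no such correlation, so these values are conditions to be met and not estimates.

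**The case against.** The strongest objection is that no stated figure is wrong. The 11 per group reproduces, and the d=0.7 sentence claims no power, so the shortfall appears only once 0.8 is carried over from another calculation. That is correct, and the conclusion is conditional on it. If 0.8 does not apply, however, the statement about d=0.7 has no power basis at all and needs the same repair.

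A second point is that d=0.7 is attributed to a source on suicidal ideation, and that SSI severity is among the primary outcomes in the Statistics section as well as in Design. Both are true, so the effect size itself is tied to the right kind of outcome. Neither supplies a power or a sample size.

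Third, the plan does not name an unadjusted t-test, and modest adjustment would close the gap at 30 v 30. This stands as a limit on the claim. But the plan does not commit to adjusting for baseline SSI. Covariates enter only if they correlate with both predictors and outcome, and the analysis is then run with and without them.

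Fourth, at 30 v 30 the gap is four percentage points, and the larger gaps come from the unresolved allocation. That is fair, and the allocation conflict is a fault in its own right. Resolving it does not cure this point, because every resolution stays below 80%.

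Fifth, the exact powers at 11 v 11 describe a comparison that the trial does not plan overall. For 60% v 10%, 30 v 15 gives 94% (chi-square) or 91% (Fisher), and 30 v 30 gives 99% for both. This is also fair: the fault in that calculation is its outcome, not its size.

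Finally, the planned effect sizes and Bayesian results would soften the over-reading of a null p-value. They do not correct the design statement.

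**Conclusion.** The concern holds. At the only power the plan states, none of the three overall allocations is large enough for the effect the study says it was designed to detect. The shortfall from 80% is 4 percentage points at 30 v 30, 9 at 40 v 20 and 22 at 30 v 15. Separately, the one sample-size calculation in the plan concerns depression response and does not size a suicidality outcome.

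The conclusion assumes that 0.8 is the intended power, that the test is two-sided at 0.05 as stated, that the comparison is unadjusted and that no patient is lost. Dropout would widen the gap. A baseline-adjusted analysis with a sufficient correlation could close it, but none is specified. This should be fixed.

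**What to change.** Change the wording of the Description of Study Populations, the Design section, the text after the Clinician Administered Measures, and the Statistics section:

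1. Reconcile the total (60, or 30 + 15) and the allocation ratio (1:1 or 2:1). This has to come first.
2. Delete the 11-per-group sentence, or label it as a depression-response calculation that does not size the primary outcome.
3. Replace the d=0.7 sentence with the power and detectable effect for SSI change at 24 h at the chosen allocation: 76% for d=0.7 and 80% for d=0.74 (30 v 30); 71% and d=0.78 (40 v 20); or 58% and d=0.91 (30 v 15).
4. If the dichotomous outcomes stay primary, give their power from stated suicidality rates and name the test.
5. If a baseline-adjusted primary analysis is adopted, specify it, and state the assumed baseline-to-24 h SSI correlation and the standard deviation to which d refers.

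No extra patients are needed. The cost is that the stated power becomes less favourable.

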Since there is no available studies in this field using the intranasal route and considering that the highest risk times for suicidal behavior are the week after admission to an inpatient psychiatric unit and the week after discharge (Qin & Nordentoft 2005), we aim to investigate the rapid antisuicidal effects of intranasal ketamine in patients with suicidal ideation during depressive episodes with or without recent use of alcohol. We hypothesize that a single dose of intranasal ketamine will induce a rapid, robust and sustained decrease in suicidal ideation in subjects with a comorbid major depressive episode and alcohol dependence relative to only depression and placebo as defined by changes in suicidal ideation scales after 24hrs.

Objectives

Primary objective: To evaluate the rapid antisuicidal effects on a single dose of intranasal ketamine (50mg) in a sample of depression comorbid or not with alcohol abuse compared to placebo.

Secondary objectives:

- To identify clinical variables and dimensions associated with the potential antisuicidal efficacy of intranasal ketamine.
- To identify post-treatment biomarkers associated with the antisuicidal response to ketamine.
- To evaluate the role of recent alcohol abuse in the antisuicidal and antidepressant effects of ketamine
- To identify clinical and biological predictors of response to ketamine
- To evaluate safety and tolerability of intranasal ketamine

Hypothesis:

-Primary: A single dose of ketamine will induce a rapid, robust and sustained decrease in suicidal ideation in subjects with a comorbid major depressive episode and alcohol dependence relative to placebo as defined by change in SSI scale after 24hrs.

-Secondary:

- The antisuicidal efficacy of intranasal ketamine will be independent from its rapid antidepressant efficacy.
- Intranasal ketamine will present superior antisuicidal efficacy in the group with comorbid depression and alcohol compared to depression only.
- Antisuicidal response to ketamine will be correlated with changes in neurotrophic factors and inflammatory markers at one day after ketamine infusion. -Intranasal ketamine (50mg) will be safe and well-tolerated.
- Alcohol use and/or family history of alcohol abuse will be associated with better antisuicidal and antidepressants response to ketamine.

IRB NUMBER: HSC-MS-17-0903

IRB APPROVAL DATE: 10/09/2019

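### Randomisation is within two alcohol groups, but no ketamine v placebo comparison is specified to include that stratum: a nearly free gain in precision is left unused

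*Combined protocol and SAP*

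**What the plan says.** Under Design, allocation to ketamine or saline is "1 to 1 in both groups, suicide or suicide plus alcohol, with a total of 4 groups". Alcohol group is therefore the randomisation stratum.

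Under Statistics, alcohol appears only in a secondary analysis of its possible role in ketamine's effect. The random effects models described there concern change over time and responders against non-responders; neither arm nor stratum is named in them. On continuous effect measures the section says "Treatment effects may be also quantified as mean differences between groups and associated effect sizes are based on standardized mean difference". Covariates enter by a screen: a baseline variable correlated with both the predictors and the outcome is analysed twice, once with it and once without.

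Other sections bear on the stratum mix:

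- Description of Study Populations gives a total of 60. It lists 30 ketamine patients, 15 with and 15 without alcohol abuse, and "current suicidal ideation and past/recent suicide attempt under placebo (Group 2, n= 15" with no alcohol split for placebo.
- The text after the list of measures gives about two thirds ketamine and one third placebo.
- A secondary hypothesis reads "Intranasal ketamine will present superior antisuicidal efficacy in the group with comorbid depression and alcohol compared to depression only".

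**The concern.** If a factor that governs the randomisation also predicts the outcome, an analysis that leaves it out keeps the between-stratum variation in the error term. The randomisation has already removed that variation from the treatment contrast, so the standard error is larger than the design warrants and the test falls below its nominal level.

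The screen does not repair this. Allocation at 1:1 within each alcohol group makes stratum nearly uncorrelated with arm, so a strongly prognostic stratum would usually fail the requirement of correlation with the predictors (read here as treatment arm). If it passed by chance, the plan would produce two analyses and would not say which is the main one.

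At stake is precision in a trial of at most 60 patients. There is also a smaller question: whether the placebo mix is sure to match the ketamine mix.

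**Working it through.** **The plan's own sample size.** Inputs from Statistics: "All statistical tests were two-sided with an alpha set at 0.05"; a target power of 80%; and earlier trials "reporting response rates of 60% with ketamine and 10% with placebo". The two-proportion formula with unpooled variance gives (1.960 + 0.842)² × (0.6×0.4 + 0.1×0.9) / 0.5² = 10.36, rounded up to 11. This matches "Eleven patients per group are required using confidence level of 95". The figure does not depend on stratification.

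**Case 1: alcohol group shifts the outcome equally in both arms.** From the documents: d = 0.7 (Statistics), 60 patients, 1:1 within two groups. Assumed: four cells of 15, within-stratum SD of 1, 0.7 measured on that SD, and a gap g between strata of 0 to 1.0 SD. The documents give no value for g.

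- Without the stratum term, the SD is inflated by k = √(1 + g²/4). The interval widens by k − 1 and d on the total SD is 0.7/k.
- The true standard error of the difference stays at √(2/30) = 0.258, so type I error is about 2Φ(−1.96k).
- With 0.7/0.258 = 2.711 and a t quantile of about 2.00, power is about Φ(2.711 − 2.00k). With the stratum term, k = 1.

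| g (assumed) | k | Interval wider by | Type I error, no stratum term | Power, no stratum term | Power, with it | d on total SD |
|---|---|---|---|---|---|---|
| 0 | 1.000 | 0% | 5.0% | 76% | 76% | 0.700 |
| 0.5 | 1.031 | 3.1% | 4.3% | 74% | 76% | 0.679 |
| 0.8 | 1.077 | 7.7% | 3.5% | 71% | 76% | 0.650 |
| 1.0 | 1.118 | 11.8% | 2.8% | 68% | 76% | 0.626 |

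Simulated t-tests and linear models agree to within about 0.3 points on type I error and 1 point on power. The mean estimate is 0.70 with or without the term, so there is no bias.

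**Case 2: alcohol alters only the ketamine response.** This is what the secondary hypothesis predicts. Put the gap g in the ketamine arm alone and keep the average effect at 0.7.

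- Residual variance without the term is the mean of (1 + g²/4) and 1, which is 1 + g²/8.
- A common stratum term leaves each cell mean off by g/4, giving 1 + g²/16.
- At g = 1.0 the ratio of standard errors is √(1.125/1.0625) = 1.03. Simulated power is 72% without the term and 74% with it. At g = 0.5 the difference is under one point.

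**Case 3: the placebo mix differs from the ketamine mix.** Under a Case 1 gap, the unadjusted difference is off by g × (placebo alcohol share − ketamine alcohol share). With ketamine 15/15 and placebo 8/7, that is g × (8/15 − 1/2) = 0.033g, or 0.02 to 0.03 SD for g of 0.5 to 1.0. Under 1:1 within strata it is zero.

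**Why the weights need stating.** An additive stratum term weights each stratum by n₁n₀/(n₁ + n₀). For ketamine 15/15 and a purely illustrative placebo split of 5/10, the weights are 15×5/20 = 3.75 and 15×10/25 = 6, or 0.385 and 0.615. Under Case 2 with g = 1.0 the stratum effects are 1.2 and 0.2, so the adjusted estimate is 0.385×1.2 + 0.615×0.2 = 0.585, about 0.12 SD below the equally weighted 0.70.

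**The case against.** The strongest reply is that the harm is small, in the safe direction and dependent on an assumption. The documents give no prognostic gap by alcohol group. The hypothesis they do state is an interaction, under which the stratum term gains little, and with an uneven placebo mix an additive term alone can move the estimate away from the equally weighted effect. Alcohol is also analysed, as a secondary question. All of this stands. It limits the size of the point and shapes the fix, but the main comparison still lacks the stratum.

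A reader might infer three stronger things, which the documents do not support:

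- **That the plan commits to an unstratified primary estimate.** The effect-size sentence offers an optional extra summary and does not mention adjustment. The section also names yes/no primary outcomes, for which no loss has been calculated here.
- **That Cohen's d would be understated.** A d on the total SD is a valid quantity that differs from a d on the within-stratum SD. The gap is only that the plan does not say which is meant.
- **That any uneven placebo mix biases the result.** Design makes the mixes match. Bias needs a mix that differs by plan and a stratum that predicts outcome under placebo. No lopsided split appears anywhere; Description of Study Populations simply gives none for placebo.

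**Conclusion.** The point holds as a low-cost improvement. It is not a threat to validity. The alcohol stratum governs the randomisation, no ketamine v placebo comparison is specified to include it, and the confounder screen would normally leave it out.

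With balanced cells at 30 v 30, omitting it costs nothing if alcohol group does not predict SSI change, and up to about 8 power points and a 12% wider interval if the strata differ by 1.0 SD. If alcohol changes only the ketamine response, the cost is about 0 to 2 points. These sizes rest on assumed gaps, a continuous outcome and a within-stratum effect of 0.7. Bias remains only a possibility, because the allocation statements conflict and the placebo split is missing; an 8/7 split would mean about 0.02 to 0.03 SD.

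**What to change.** In Statistics:

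1. Include the alcohol randomisation stratum as a fixed term in every ketamine v placebo comparison of SSI and MADRS change, whatever its correlation with arm and outside the confounder screen.
2. For yes/no outcomes, use a stratum-weighted risk difference.
3. Pre-specify the stratum weights, for example equal weights, and show the treatment estimate in each stratum beside the combined one.
4. State which SD standardises Cohen's d.

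Elsewhere, reconcile Design (1:1 within each alcohol group), Description of Study Populations (a total of 60, but 30 + 15 = 45 listed) and the two-thirds/one-third statement after the list of measures, and give the placebo number per stratum.

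The cost is wording and one degree of freedom in each model. No new data or patients are needed, and at a gap of zero the extra term leaves power at 76%.
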